- v) To measure changes in health and skill related components of fitness (vertical jump, hand-grip strength, knee extensor muscular strength and aerobic fitness) throughout an academic sporting season.
- vi) To measure any incidence of injury and illness that occurs between winter and spring and its correlation with Vitamin D status, training and bone health.
- vii) To ascertain whether there are any differences in the research outcomes between trained and control subjects

Hypothesis

We propose that athletes will have a sub-optimal (<50 nmol/l) of 25 (OH) D status at baseline and a poor vitamin D status (lowered plasma 25(OH)D) during the spring as a result of lower daylight exposure during the winter period. In addition to this we assume that those who regularly compete and train indoors will have a lower Vitamin D status at baseline due to insufficient exposure to ultraviolet B radiation from the Sun.

Study design

The D-BIICEP Study is an observational study. Participants will be assessed at baseline in winter (September/October) and again at the end of the observational period in spring (March/April).

Outline of Study

- **Pre-screening:** screening questionnaire is administered to participant.
- **Session 1:** Consent forms to be signed. pQCT test and weight, height and body composition. Hip and femoral head DEXA scan. Jump height and maximal oxygen uptake ($VO_{2\text{ max}}$) test.
- **Session 2:** Plasma samples collected and muscular strength tests performed.

20 weeks of training/ competition for their respective University Sport Team or regular physical activity levels for the control subjects.

Participants are expected to complete their Illness and Injury Questionnaire

- **Session 3:** pQCT test, weight, height and body composition. Hip and femoral head DEXA Scan. Jump height and maximal oxygen uptake ($VO_{2\text{ max}}$) test.
- **Session 4:** Plasma samples collected and muscular strength tests performed

Trial Visit Activities

During this study the subjects will be asked to visit the labs on two occasions, at the beginning of the study for baseline measurements, and again on two occasions at the end of the study.

At both trial visits, participants will have the following outcomes assessed:

- Sport performance: Vertical jump height, muscular strength and aerobic fitness
- Peripheral Quantitative Computed Tomography (pQCT) scan of the bone mineral composition of the tibia.

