Upon commencing the study, the participants will be required to track their incidence of illness and training habits during the 20-week experimental period between baseline and conclusion measurements. Throughout this period they must record the incidence of illness and days trained during the months in a check-list booklet, which will be provided to them. An email reminder will be sent to prompt all participants to complete these booklets on a daily basis during the experimental period, this should only take 1-2 minutes every evening. Throughout the duration of the trial, the participants will be contacted via telephone/ email on a monthly basis to discuss any issues and maintain good communication.

Recruitment

Participants will be recruited from the University of Surrey; posters will be positioned around the Stag Hill campus, Manor Park Campus and Hazel Farm. Flyers will be placed in communal areas, the students' union, the university library and at Surrey Sports Park to promote awareness for the study. In addition to this, a brief presentation will be given to students following their lectures in the same format as the poster or flyer.

Coaching staff and the signatories of Team Surrey committees will also be approached for the study and flyers will be provided to hand out to their team members if they are keen to complete this as a team. Social media sites such as Facebook will be used to publicise the study: the poster or flyer will be inserted as a photo with permission of the administrator of the Facebook pages.

If the individual is interested in participating in the study after reading the information sheet, they will contact the investigator and session 1 will be arranged. A member of the research team will inform the participant of all aspects pertaining to participation in the study before consent is sought.

Children, and other vulnerable groups, including those unable to provide informed consent will not be recruited. Moreover, we do not have access to translator or interpreter services, so will not recruit those who do not have a good understanding of the English language either in written or oral form.

It will be explained to the potential participant that entry into the study is entirely voluntary and that they can withdraw at any time. In the event of their withdrawal it will be explained

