that their data collected so far could be erased, but we will seek their consent to use the data collected up to the point of withdrawal in the final analyses where appropriate.

University Athlete Inclusion criteria

- Male or female
- Aged 18-30
- Regularly train/compete for Team Surrey Basketball, Boat Club, Swimming and Waterpolo, Netball or Rugby (for more than 4 hours/week)
- In good physical health
- Have a BMI >18 kg/m²
- Able to provide written informed consent

Control Group Inclusion Criteria:

- Male or Female
- Age 18-30
- Do **not** use sun beds/ will not be going on a sun holiday/ returning home to a traditional sun holiday location between February 2017 and October 2017. This is because the results will be used to represent the Vitamin D status of young sporting individuals residing within the UK during these seasons.
- Do **not** take supplements containing Vitamin D
- Do **not** compete for Team Surrey and exercise less than 150 minutes / week.
- BMI: 18 – 30 kg/m²

Exclusion criteria

- Currently receiving treatment for medical conditions that are likely to affect vitamin D metabolism
- Hypercalcaemia (>2.5mmol/L)
- Regular use of sun-beds
- Having a sun holiday one month prior to commencing the study or plans for a sun holiday within the study period or will be returning home to a sun holiday location.
- Use of vitamin supplements containing vitamin D (if the prospective participants agrees to stop Vitamin D supplementation to join the study, a wash-out period of 8 weeks prior to commencing the trial would be acceptable).
- Excess alcohol intake for participants aged 18 years (> 21 units for males, > 14 units for females per week, as per Government guidelines)
- Those under dietary restriction (except vegetarianism) or following a weight-reducing diet.
- Clinically significant haematological abnormalities other than mild anaemia (Hb <12.0g/dl)
- Active malignancy
- Pregnant or planning a pregnancy during the study period

If a participant is subsequently found to be ineligible for the study their screening questionnaire will be destroyed due to the questionnaire containing sensitive information.

Participant Withdrawal

All participants will be notified during the consenting process that they are free to withdraw from the trial at any time, without giving a reason.

Participants will be withdrawn from the trial by the Principal Investigator if:

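### Athletes may return from a sun holiday one month before a September/October baseline, against 8 weeks for supplements, so holiday vitamin D may raise baseline 25(OH)D and enlarge the seasonal fall

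*Combined protocol and SAP*

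**What the plan says.** The Exclusion criteria rule out "Having a sun holiday one month prior to commencing the study or plans for a sun holiday within the study period". The same list excludes users of vitamin D supplements, but lets them in if they stop: "a wash-out period of 8 weeks prior to commencing the trial would be acceptable". No reason is given for the different lengths.

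Study design gives the timing: "Participants will be assessed at baseline in winter (September/October) and again at the end of the observational period in spring (March/April". The section on tracking illness and training puts the two measurements 20 weeks apart: "during the 20-week experimental period between baseline and conclusion measurements". The Hypothesis expects athletes to be below 50 nmol/l at baseline and to show "a poor vitamin D status (lowered plasma 25(OH)D) during the spring as a result of lower daylight exposure during the winter period". The Synopsis names 25(OH)D as the primary endpoint.

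The Control Group Inclusion Criteria add a ban on sun beds, sun holidays or "returning home to a traditional sun holiday location between February 2017 and October 2017", on the ground that "the results will be used to represent the Vitamin D status of young sporting individuals residing within the UK during these seasons". The athlete inclusion list has no such item, although the stated reason speaks of sporting individuals.

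The listed assessments include no record of sun exposure or travel. The statistics section plans an ANOVA of pre against post and names no covariate.

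**The concern.** Sun holidays and supplements are both excluded because they add vitamin D from outside the exposure under study. The protocol clears one source for 8 weeks and the other for about a month, and the shorter window falls just after summer. An athlete back from a late-summer sun holiday is therefore eligible and may still carry a surplus when baseline blood is taken.

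The direction of any effect is known. A surplus raises baseline, is mostly gone 20 weeks later, and so enlarges the fall that the plan attributes to winter daylight. It also adds noise to the baseline indoor/outdoor contrast, or bias if holiday-taking differs by sport. If controls were kept from sun holidays all summer and athletes were not, the trained-versus-control comparison (objective vii) is affected too.

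Separately, the September/October time point is labelled winter. Objectives i, ii and vi use that label without months, so an end-of-summer value could be reported as winter status.

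**Working it through.** **1. The plan's own figure.** The plan gives no carry-over figure. The nearest number is the minimum of 52 subjects for a 35% seasonal difference at 80% power. It cannot be reproduced, because neither the baseline mean nor the SD of the within-person change is stated. Back-solving, two-sided:
- read as 52 pairs, it implies a standardised change of 0.396, which cannot be put into ng/mL without the SD of change;
- read as two groups of 26, it implies d = 0.792, and 0.792 × 13.2 = 10.5 ng/mL, which is 35% of an assumed mean of about 30 ng/mL.

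The second reading serves only as a yardstick.

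**2. Dates.** One month is about 30 days and 8 weeks is 56, a gap of 26 days. For follow-up to start on 1 March after 140 days, baseline cannot be before about 12 October. An athlete tested on 12 October may have returned about 12 September; 8 weeks would mean 17 August. For a test on 31 October the dates are about 30 September and 5 September. So the shorter window admits late-summer holidays.

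**3. Share of a holiday rise remaining.** Assume first-order loss, f(t) = 0.5^(t / half-life). The net contribution to the fall is f(t) − f(t + 140).

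| Half-life (days, assumed) | f(30) | f(56) | Net, 30 days | Net, 56 days |
|---|---|---|---|---|
| 14 | 0.23 | 0.06 | 0.23 | 0.06 |
| 21 | 0.37 | 0.16 | 0.37 | 0.16 |
| 28 | 0.48 | 0.25 | 0.46 | 0.24 |
| 42 | 0.61 | 0.40 | 0.55 | 0.36 |
| 60 | 0.71 | 0.52 | 0.57 | 0.42 |

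**4. Inflation of the mean fall** = p × B × net share, where p is the proportion who returned just outside the window (assumed 10 to 50%) and B is the holiday rise (assumed 4 to 12 ng/mL).
- Lowest: 0.10 × 4 × 0.226 = 0.09 ng/mL, or 0.01 of the SD of 13.2.
- Middle (half-life 28 days, p = 25%, B = 8): 0.25 × 8 × 0.46 = 0.92 ng/mL, or 0.07 SD.
- Highest: 0.50 × 12 × 0.567 = 3.40 ng/mL, or 0.26 SD.

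With a gap of 56 days the range is about 0.02 to 2.5 ng/mL. A longer look-back reduces the carry-over but does not remove it. All travellers are placed exactly at the edge of the window, so for a given p and B these are upper values. The SD is the one the Synopsis quotes for the indoor/outdoor comparison, not an SD of change.

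**5. Against the yardstick.** 3.4 / 10.5 = 32% at the extreme and 0.92 / 10.5 = 9% in the middle case.

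**6. Controls.** If baseline is autumn 2017, the February to October 2017 ban covers the whole preceding summer for controls only. The inflation in step 4, with p taken among athletes, would then pass undiluted into the athlete-control difference in change. If baseline is autumn 2016, the ban does not cover the preceding summer and controls share the athletes' gap. The documents do not settle which year applies.

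**The case against.** - **The windows need not match.** One is a look-back for a holiday, the other a concession to people who would otherwise be excluded. A reader might infer a contradiction, but the protocol never says that the two sources need equal clearance. This stands: 8 weeks is only the plan's own benchmark.
- **The size is assumed throughout.** This also stands. A reader might infer that carry-over is established, or that it makes up much of the seasonal fall. For one traveller with an assumed rise of 20 nmol/l, 4.5 to 10 nmol/l remains at 30 days (half-life 14 to 30 days), which is 26 to 57% of a 35% fall from 50 nmol/l (17.5). That describes one unfavourable participant. If 20% were such travellers, the mean would move by 0.9 to 2.0 nmol/l, or 5 to 11%.
- **A raised baseline is conservative.** True for the hypothesis of below 50 nmol/l, which it cannot falsely confirm. It is not true for the seasonal fall, where the bias favours the hypothesis.
- **A high end-of-summer value is expected.** Correct. Vitamin D from ordinary UK sun is part of the contrast under study; only the holiday surplus is not.
- **Controls are already covered.** Only if baseline is autumn 2017, and then the groups have unequal criteria.
- **Nothing shows that holiday-taking differs by sport.** Also correct, so bias in the indoor/outdoor contrast is only a possibility.
- **The months are printed beside the winter label.** They are in Study design, but not in the objectives. Relabelling is a wording matter and does not reduce carry-over.

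The screening questionnaire is not reproduced and may well ask about holidays. Even so, nothing in the plan carries a return date into the analysis.

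**Conclusion.** The concern holds in a limited form. For athletes, the protocol permits a late-summer sun holiday shortly before a post-summer baseline, and no planned covariate or sensitivity analysis would detect or correct a surplus in the primary endpoint. The surplus may carry over; the documents do not show that it does. Under the assumed ranges the mean fall is inflated by about 0.1 to 3.4 ng/mL (0.01 to 0.26 SD). This could overstate the seasonal result but is unlikely to create it, since even the top value is about a third of the 10.5 ng/mL implied by one reading of the sample size. That comparison rests on first-order loss, on the assumed half-life, rise and share of travellers, and on reading 52 as two groups of 26.

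The mismatch between athlete and control sun criteria needs no such assumptions. The passages and their dates must be reconciled, because on one reading they can confound objective vii. The point deserves correction because the direction of bias is known and the remedy is cheap.

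**What to change.** 1. Reconcile the athlete and control sun criteria and their calendar dates with the September/October to March/April schedule. Apply one look-back to both groups, and either align it with the 8-week supplement wash-out or state why it differs.
2. Record the return date of the last sun holiday at screening. Repeat the baseline indoor/outdoor and seasonal-change analyses without participants who returned within 8 weeks, or adjust for time since return. This is needed even with a longer look-back, since some carry-over may remain at 56 days.
3. Describe September/October as autumn (end of summer) in the design and in objectives i, ii and vi.

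Travellers should not be booked systematically later in the window. With 20 weeks to a March start, baseline can run only from about 12 to 31 October, which is 19 days against a 26-day gap. Later booking would also tie holiday status to calendar date while UK sun is declining.

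The cost is one screening field, one sensitivity analysis, a few lines of text and, if the look-back is lengthened, a small recruitment loss.

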**The Inter-relationship between Vitamin D: Bone, Illness,
Injury and its Impact on Exercise Performance**
(The D-Biicep Study)

Study personnel and contact details

Principal investigator:

[name]
Department of Nutritional Sciences
Faculty of Health & Medical Sciences,
University of Surrey, Stag Hill campus
[name]
[contact]
Email: [contact]

Co-investigators:

[name] (PhD student)
Department of Nutritional Sciences
Faculty of Health & Medical Sciences
University of Surrey, [name]
[contact]
Email: [contact]

[name]
Department of Nutritional Sciences
Faculty of Health & Medical Sciences
University of Surrey, Manor Park Campus
[name]
[contact]
Email: [contact]

[name]
Department of Nutritional Sciences
Faculty of Health & Medical Sciences
University of Surrey, Manor Park Campus
[name]
[contact]
Email: [contact]

Synopsis

Title	The Inter-relationship between Vitamin D: Bone, Illness, Injury and its Impact on Exercise Performance
Acronym	The D-BIICEP Study
Chief Investigator	[name]
Objectives	To explore the inter-relationship between vitamin D status, calcium homeostasis, bone health, injury, illness and sport performance in young active adults.
Study Configuration	Assessment of vitamin D status, muscular strength, endurance capacity, body composition and bone mineral density in healthy university level athletes before and after 20 week of competitive training and non-trained control subjects before and after 20 weeks.
Setting	The Clinical Investigative Units (CIU), Department of Nutritional Sciences, University of Surrey Surrey Human Performance Institute (SHPI), Surrey Sports Park, Guildford
Sample size estimate	Sample size calculation is based on detecting a mean difference in 25 (OH) D status (study primary endpoint) between indoor and outdoor athletes, considering the standard deviation (13.2 ng.mL) and effect size (0.48) reported previously (Halliday et al 2011). To give 80% power and a significance level P < 0.05 the study will be conducted with 18 participants in each arm. To allow for 15% dropout 63 participants will be recruited
Number of participants	63 subjects; 21 trained males, 21 trained females and 21 controls(male and female)

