1. The participant develops a medical condition or becomes pregnant either prior to entering the study or during, which may adversely affect the outcome of the study.
2. It is clearly demonstrated that the participant is non-compliant completing study activities and the control procedures requested of them.
3. If the participant suffers an serious adverse event

All data prior to subject withdrawal will be used in analysis; unless the participant specifically requests that their data is not to be used. Withdrawn participants will not be replaced as an anticipated drop-out rate of 15% has been accounted for in the recruitment targets.

Informed consent

All participants will provide written informed consent for participation, and use and retention of the study data. The Consent Form will be signed and dated by the participant before they enter the study. The Investigator will explain the details of the study and provide a Participant Information Sheet and a DEXA information folder, ensuring that the participant has sufficient time to consider participating or not. The Investigator will answer any questions that the participant has concerning study participation.

Informed consent will be collected from each participant before they undergo any interventions (including physical examination and history taking) related to the study. One copy of this will be kept by the participant and one will be kept by the Investigator.

Those incapable of providing valid consent will not be recruited. Participants under the age of 18 will not be recruited.

Statistics, Sample size and justification

Statistical analysis based on preliminary data from our group and Halliday et al (2011) indicates that a minimum of 52 subjects is required in order to detect a 35% difference in vitamin D concentrations across seasons at a power of 80%, significance level $P<0.05$.

In order to achieve an equal division between genders, 26 males and 26 females from different indoor and outdoor sports across Team Surrey need to be recruited. Based on our preliminary study we are expecting a 15% drop out. We will therefore aim to recruit 63 subjects (21 females, 21 males and 21 sedentary controls, males and females).

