Descriptive data ((25(OH)D status, jump height, muscular power, muscular strength, $VO_{2\ max}$, fat, lean and bone mass) will be expressed as the group mean ($\pm SD$) or as the median (inter-quartile range) if the data are non-parametric. Comparison of pre- and post-training periods will be made using ANOVA.

Quality assurance & audit

Insurance and indemnity

The University of Surrey has taken out an insurance policy to provide indemnity in the event of a successful litigious claim for proven non-negligent harm.

Study conduct

The study coordinator/local investigator, or where appropriate, a nominated designee of the sponsor, shall carry out site and study audits.

Study data

Monitoring of study data shall include confirmation of informed consent prior to inclusion; calculating and checking prior exposure to ionising radiation; data storage and data transfer procedures; local quality control checks and procedures, including QA scans, and back-up of any local databases. A nominated designee of the study team, shall carry out monitoring of study data as an ongoing activity.

Data Handling

The Principal Investigator will act as custodian for the trial data. The following guidelines will be strictly adhered to:

- Participants data will be completely anonymised
- All anonymised data will be stored in a secure location on the University's servers and on a password-protected computer these will be in line with best practice as recommended in the University of Surrey Research and Information Governance policies.
- All trial data will be stored and archived as indicated by The Medicines for Human Use (Clinical Trials) Amended Regulations 2006.
- When a subject does not meet the inclusion criteria, all questionnaires and collected data will be destroyed.

Record retention and archiving

In compliance with the ICH/GCP guidelines, regulations and in accordance with the University of Surrey Code of Research Conduct and Research Ethics, the Chief or local Principal Investigator will maintain all records and documents regarding the conduct of the study. These will be retained for at least 7 years or for longer if required. If the responsible investigator is no longer able to maintain the study records, a second person will be nominated to take over this responsibility.

Statement of confidentiality

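### The pre/post ANOVA has no stated form and no rule for a missing spring visit; a mixed model on all available visits would keep the pairing and remove baseline-related drop-out bias at no extra cost

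*Combined protocol and SAP*

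**What the plan says.** Participant Withdrawal: "All data prior to subject withdrawal will be used in analysis", unless the participant asks otherwise, and "Withdrawn participants will not be replaced as an anticipated drop-out rate of 15% has been accounted for in the recruitment targets". The Recruitment section adds a qualification: consent is sought to use data up to withdrawal in the final analyses where that is appropriate.

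Statistics, Sample size and justification: "a minimum of 52 subjects is required in order to detect a 35% difference in vitamin D concentrations across seasons", at 80% power, and "Based on our preliminary study we are expecting a 15% drop out". The recruitment target is 63, made up of 42 athletes and 21 controls.

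The Synopsis and the end of the Statistics section each name one inferential method: "Comparison of pre- and post-training periods will be made using ANOVA". It follows a list of descriptive outcomes covering vitamin D, strength, aerobic capacity and body and bone mass.

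Under Study design there are two measurement occasions, one in September/October and one in March/April. Nothing says whether the ANOVA is within or between participants, who is in the analysis set, or what happens when the spring visit is missing.

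**The concern.** With only two visits, the form of the ANOVA decides what happens to people who leave. A classical repeated-measures ANOVA needs both values, so a participant with a baseline and no spring visit contributes nothing to the estimated change. A between-groups ANOVA of all first values against all second values keeps those baselines, but treats two measurements on one person as independent.

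The seasonal change is the one comparison for which a test is named, so the choice matters. Drop-out may well be informative: the investigator withdraws people for a medical condition, pregnancy, non-compliance or a serious adverse event, while illness and injury are themselves study outcomes. If leavers differ at baseline, a completers-only change does not estimate the change in the enrolled group. An unspecified form also leaves the choice open until the data have been seen.

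**Working it through.** **1. The plan's own numbers.** 63 x 0.15 = 9.45 expected drop-outs and 63 x 0.85 = 53.55 remaining, so about 9 lost and 54 pairs left (53 if rounded down). The stated minimum is 52, and 52/0.85 = 61.2, which rounds up to 62. By the Synopsis route, 18 x 1.15 = 20.7, or 21 per arm, and 3 x 21 = 63. The target therefore roughly covers the lost pairs. The 52 itself cannot be recomputed, because no seasonal mean, SD or correlation is given.

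**2. Inputs for the standard errors.** N = 63 baselines and n = 54 spring values. The SD comes from the Synopsis ("considering the standard deviation (13.2 ng.mL) and effect size (0.48) reported previously"), where it serves the indoor/outdoor comparison. I assume it applies at both visits and convert with an assumed factor of 2.5: 13.2 x 2.5 = 33 nmol/L. The within-person correlation r is not in the documents, so I use a range. Athletes and controls are pooled.

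**3. Standard error of the mean change, in SD units.**

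- Paired, completers only: sqrt(2(1-r)/54)
- Mixed model, all visits: sqrt((1-r²)/54 + (1-r)²/63)
- Between groups, as reported: sqrt(1/63 + 1/54) = 0.185

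| r | paired | mixed | saving from mixed | between/paired |
|---|---|---|---|---|
| 0.3 | 0.161 | 0.157 | 2.5% | 1.15 |
| 0.5 | 0.136 | 0.134 | 1.8% | 1.36 |
| 0.7 | 0.105 | 0.104 | 1.1% | 1.76 |
| 0.8 | 0.086 | 0.085 | 0.7% | 2.15 |

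**4. Bias when drop-out depends on baseline.** Let drop-outs start 0.5 to 1 SD below completers (assumed), with spring values regressing on baseline with slope r. Completers then have a baseline mean above the enrolled mean by 0.15 x gap.

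- Completers-only bias = (r-1) x 0.15 x gap. At r=0.5: -0.5 x 0.15 x 16.5 = -1.2 and -0.5 x 0.15 x 33 = -2.5 nmol/L. At r=0.7: -0.7 and -1.5 nmol/L. The fall is overstated.
- Between-groups bias = +r x 0.15 x gap. At r=0.5: +1.2 to +2.5 nmol/L. At r=0.7: +1.7 to +3.5 nmol/L. The fall is understated.

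Against the paired standard error at r=0.5 (0.136 x 33 = 4.5 nmol/L), the completers-only bias is 0.28 to 0.55 of one standard error. If the plan's 35% is applied to an assumed mean of 50 nmol/L, the fall is 17.5 nmol/L and the bias is 7-14% of it.

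**5. Power if pairing were ignored.** The test rejects when the difference exceeds 1.96 x 0.185 = 0.363 SD. The true sampling standard error of that difference is sqrt(1/63 + 1/54 - 2r/63), which is 0.136 at r=0.5 and 0.110 at r=0.7. A fall of 17.5 nmol/L is 17.5/33 = 0.53 SD. Then (0.530-0.363)/0.136 = 1.23, giving 89% power at r=0.5; at r=0.7 the value is 1.51, giving 93%. The paired analysis gives 97% and 99.9%.

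**The case against.** A reader might infer that the withdrawal rule and the ANOVA contradict each other. The documents do not support that. The rule speaks of analysis in general, the Recruitment section limits use to where it is appropriate, and a withdrawn participant's baseline has clear uses in the descriptive summaries and in the two baseline hypotheses (status below 50 nmol/l, and lower status in indoor athletes). Nor does the bare word ANOVA exclude a version that uses all available data.

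A reader might also infer a severe loss of power. Between-groups power does fall to 46% (r=0.5) or 45% (r=0.7) for a change of 0.35 SD, but the protocol's 35% is a difference in concentration, not 0.35 SD. At 17.5 nmol/L even the unpaired test stays above the planned 80%, as step 5 shows. The design measures the same people twice, so a within-person ANOVA is the natural reading, and on that reading the mixed model gains little precision.

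It is also fair to say that the size of the bias is hypothetical, since the documents give neither a baseline gap nor a correlation, and that a mixed model removes it only if data are missing at random, which the withdrawal reasons could call into question. These objections stand as limits on the size of the point. They do not supply the missing specification, and the existing method has no advantage over the proposed one.

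**Conclusion.** The point holds as an unspecified analysis with a better alternative available at no cost in data. On the natural paired reading, about 9 of 63 participants drop out of the seasonal comparison. The precision lost is minor and roughly budgeted. The bias is moderate: -1.2 to -2.5 nmol/L at r=0.5 and -0.7 to -1.5 nmol/L at r=0.7. It rests on a baseline gap of 0.5 to 1 SD, SD 33 nmol/L, 15% drop-out and drop-out that depends on baseline only. The inflated standard error arises only if pairing is ignored, which the documents do not say will happen.

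The budgeting statement takes the 52 as counting all participants. The Statistics section describes the 52 as 26 male and 26 female team athletes, while only 42 athletes are to be recruited (42 x 0.85 = 35.7 completers). That is a separate inconsistency and is not needed for this point.

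**What to change.** Replace the ANOVA sentence in the Synopsis and in the Statistics section with a linear mixed model for each repeated outcome, fitted by REML to all available visits. Use visit, group (trained or control) and visit-by-group as fixed effects and participant as a random effect. The group terms are needed because secondary objective vii compares trained and control subjects.

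Report the pre/post change with a 95% confidence interval. State that the analysis assumes data are missing at random, tabulate baseline characteristics of completers and drop-outs, and give the completers-only result as a sensitivity analysis.

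The cost is a few sentences of analysis wording. No further visits, measurements or participants are needed.

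### The sample-size section says 26 male and 26 female athletes must be recruited but plans 21 and 21, so its 80% power statement is not supported for the athletes

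*Combined protocol and SAP*

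**What the plan says.** Three statements follow one another in the section Statistics, Sample size and justification:

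- **Size needed:** "a minimum of 52 subjects is required in order to detect a 35% difference in vitamin D concentrations across seasons", at 80% power and a 5% significance level.
- **Who they are:** for an even split by sex, "26 males and 26 females from different indoor and outdoor sports across Team Surrey need to be recruited".
- **What will be recruited:** after a 15% dropout allowance, "We will therefore aim to recruit 63 subjects (21 females, 21 males and 21 sedentary controls, males and females").

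The synopsis gives the same split and makes clear that the two groups of 21 are the athletes: "21 trained males, 21 trained females and 21 controls(male and female"). The Participant Withdrawal section adds that "Withdrawn participants will not be replaced as an anticipated drop-out rate of 15% has been accounted for in the recruitment targets". One control-group inclusion criterion reads "Do not compete for Team Surrey and exercise less than 150 minutes / week".

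The synopsis reaches the same total of 63 by another route: 18 per arm to compare indoor with outdoor athletes, with an allowance for 15% dropout.

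**The concern.** A dropout allowance can only raise a recruitment target. Here the number of athletes of each sex falls from 26 to 21 when it is applied. The total rises from 52 to 63 only because a third group has been added, and that group cannot contain Team Surrey athletes.

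This section justifies the size of the study, and a reader cannot tell from it whether the powered sample is 52 athletes, the 42 athletes recruited, or a pool of athletes and controls. If it is athletes, the plan does not deliver the number the section calls necessary, and the assurance that dropout is already covered does not hold for them. If it is the pool, the text does not say so and describes the wrong people.

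**Working it through.** **Inputs from the protocol.** Required: 52, described as 26 + 26 Team Surrey athletes. Recruited: 21 + 21 athletes and 21 controls. Dropout: 15%, without replacement. Power 80%, significance level 5%, sidedness not stated.

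**The stated figures.** The 52 cannot be reproduced, because no mean, SD of change or within-person correlation is given for the 35% difference. The 63 can be reached in two ways, and the protocol does not say which was used:

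- 52 / 0.85 = 61.2, so 62, rounded up to three groups of 21 = 63;
- the synopsis figure, 18 × 1.15 = 20.7, so 21, and 21 × 3 = 63. (Dividing by 0.85 instead gives 21.2, so 22, and 22 × 3 = 66.)

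**Counts.**

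| | Stated as needed | Recruited | Expected to finish (× 0.85) |
|---|---|---|---|
| Athletes, each sex | 26 | 21 | 17.85 |
| Athletes, total | 52 | 42 | 35.7 |
| All participants | – | 63 | 53.55 |

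- Shortfall at recruitment: (52 − 42) / 52 = 19%.
- Shortfall at completion: (52 − 35.7) / 52 = 31%. This takes 52 as a completer target, which the later dropout allowance suggests but the text does not state.
- Recruitment needed for 52 athletes to finish: 26 / 0.85 = 30.6, so 31 per sex, 62 in all; 62 − 42 = 20 more than planned.

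**What the shortfall could mean for power.** These are illustrations, not bounds. In each case the standardised effect is solved so that the stated sample gives exactly 80%, and power is then recomputed for a paired t-test (noncentral t, two-sided 5%). The paired test, the sidedness and the correlations r are assumptions.

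- *52 is a number of pairs.* Implied effect 0.396 SDs of change. Power is 64% with 36 athletes, 71% with 42, and 81% to 82% with 53 to 54 if controls are pooled. With a one-sided 5% test (implied effect 0.349) it is 66% with 36 and 81% with 54.
- *52 meant 26 against 26 independent values.* Implied d = 0.792. The paired effect is d / √(2(1 − r)). With 36 pairs, power is 83% at r = −0.25, 90% at r = 0 and above 99% at r = 0.5.
- *52 meant 52 against 52 independent values.* Implied d = 0.555. With 36 pairs, power is 53% at r = −0.25, 63% at r = 0, 75% at r = 0.25 and 90% at r = 0.5.

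The range runs from about 53% to above 99%, so the document does not allow a reader to say what power the athletes have.

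**The case against.** The best defence is that the 52 refers to all participants. The 80% sentence speaks of subjects, not athletes, and the 26 + 26 sentence is offered as a way to balance the sexes, not as a condition for power. Controls are also measured twice: the synopsis lists "non-trained control subjects before and after 20 weeks". On that reading 63 × 0.85 = 53.6 covers 52, the power sentence stands, and only the Team Surrey sentence is wrong.

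This reading is possible, and the documents do not rule it out. Against it, 26 + 26 is exactly 52 and is assigned to Team Surrey. The seasonal hypothesis is about athletes ("athletes will have a sub-optimal (<50 nmol/l) of 25 (OH) D status at baseline and a poor vitamin D status"), and secondary objective vii treats controls as a comparison group. The planned ANOVA of pre- and post-training values does not say whether controls enter. Even if the defence is accepted, the 80% belongs to a pooled sample and still says nothing about athletes alone.

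Two further points are fair. The section does name ANOVA for the analysis; what it lacks is the test behind the power calculation. If that ANOVA is within-person with two time points, it matches a two-sided paired t-test, so the one-sided illustration carries little weight. Also, no loss of power has been demonstrated, the study is observational, and the synopsis ties its primary endpoint to indoor versus outdoor athletes, which argues for a lower severity. That limits what may be claimed about the study, but it does not make the sample-size text correct.

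**Conclusion.** The concern holds. The plan recruits 42 athletes where the same section says 52 are needed, and about 36 are expected to finish. The sentence requiring 26 of each sex from Team Surrey conflicts with the recruitment plan on every reading, and the 80% power statement is not supported for the athletes. The total of 63 supports it only for athletes and controls together.

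The counts rest only on the protocol's own figures. The 31% shortfall also takes 52 as a completer target. The power figures depend on assumptions the protocol does not supply and do not show that the study is underpowered. The correction is nevertheless essential, because this statement justifies the study's size and is wrong as written.

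**What to change.** First decide, and state, whether the 52 means athletes only or all participants, and whether controls enter the seasonal pre/post comparison. Then correct or delete the sentence about 26 males and 26 females and use the matching text.

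*If all participants:*

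> A minimum of 52 participants (athletes and controls combined) with both assessments is required. We will recruit 63 (21 male athletes, 21 female athletes, 21 controls); with 15% dropout about 54 are expected to complete, giving [recomputed] power for a 35% difference.

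*If athletes only:*

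> We will recruit 42 Team Surrey athletes (21 male, 21 female) and 21 controls; with 15% dropout about 36 athletes are expected to complete, giving [recomputed] power for a 35% difference.

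*In either case add:*

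> This assumes a baseline mean of [value], an SD of change of [value] from [source], and a [named test], [one- or two-]sided at 5%.

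Fill the brackets from the preliminary data that the section already cites, not from the illustrative powers given here. Use the same sample-size statement and the same primary contrast (season, or indoor versus outdoor) in the synopsis and in this section.

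The cost is protocol wording and one recalculation; the stated power may turn out less favourable. Recruitment changes only if the sponsor confirms that 52 athletes must finish and keeps that target: 62 athletes (31 per sex), 20 more than planned, in addition to the controls.
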